2.0 Goals

2.1 Primary

- 2.11 Phase I: To establish the maximum tolerated dose of auranofin plus sirolimus after at least one line of platinum based chemotherapy for stage IV squamous histology NSCLC for lung cancer (squamous, Ras-mutated adenocarcinoma, or small cell lung cancer) patients with no acceptable standard treatment options.
- 2.12 Phase II: To assess the progression-free survival at four months of patients treated with auranofin after at least one line of platinum based chemotherapy for lung cancer (squamous, Ras-mutated adenocarcinoma, or small cell lung cancer) patients with no acceptable standard treatment options.

2.2 Secondary

- 2.21 To assess the overall survival in this population in comparison to recent historical controls.
- 2.22 To determine the Adverse Events (AE) profile and safety of the regimen.
- 2.23 To determine the overall response rate, per RECIST criteria, and duration of tumor response in those patients with measurable disease.

2.3 Correlative Research

2.31 To assess the relationship between molecular correlates and PFS, OS, response and adverse events.

3.0 Patient Eligibility

- 3.1 Inclusion Criteria
 - 3.11 Age \geq 18 years.
 - 3.12 Histologic or cytologic confirmation of lung cancer (squamous, Rasmutated adenocarcinoma or small cell lung cancer).
 - 3.13 Patients must have received at least one course of chemotherapy consisting of a platinum doublet and must have no acceptable standard treatment options.
 - 3.14 Prior radiation therapy is permitted as long as:
 - Recovered from the toxic effects of radiation treatment before study entry, except for alopecia.
 - 3.15 The following laboratory values obtained \leq 14 days prior to registration:
 - ANC >1500 □L
 - PLT ≥100,000 □L
 - Hgb ≥9 g/dL
 - Total bilirubin ≤1.5 x upper limit of normal (ULN) or direct bilirubin <ULN
 - SGOT (AST) and SGPT (ALT) □3 x ULN or SGOT (AST) and SGPT (ALT) □5 x ULN is acceptable if liver has tumor involvement
 - 3.16 ECOG performance status (PS) 0, 1, 2. (Appendix I)

| | 3.17 | Negative serum pregnancy test done \leq 7 days prior to registration, for women of childbearing potential only. |
|-----|--------|--|
| | 3.18 | Ability to provide informed consent. |
| | 3.19a | Life expectancy □12 weeks. |
| | 3.19b | Willing to return to Mayo Clinic enrolling institution for follow-up. |
| | 3.19c | Willing to provide tissue samples for correlative research purposes (see Sections 6, 17). |
| 3.2 | Exclus | sion Criteria |
| | 3.21 | Any of the following because this study involves an agent that has known genotoxic, mutagenic and teratogenic effects. Pregnant women Nursing women Men or women of childbearing potential who are unwilling to employ adequate contraception |
| | 3.22 | Symptomatic, untreated, or uncontrolled CNS metastases or seizure disorder. NOTE: Patients with treated CNS metastases without evidence of progression and without uncontrolled symptoms or need for steroids may enroll. |
| | 3.23 | HIV-positive patients receiving combination anti-retroviral therapy are excluded because of possible pharmacokinetic interactions with oral investigational agents. |
| | 3.24 | Unwilling or unable to, comply with the protocol. |
| | 3.25 | Any of the following prior therapies: ☐ Radiation to ≥25% of bone marrow (see appendix III) |
| | | ☐ Major surgery (i.e., laparotomy), open biopsy, or significant traumatic injury ≤4 weeks prior to registration. Minor surgery ≤2 weeks prior to registration. Insertion of a vascular access device is not considered major or minor surgery in this regard. |
| | 3.26 | Any of the following concurrent severe and/or uncontrolled medical conditions: ☐ Hypertension, labile hypertension, or history of poor compliance with antihypertensive medication ☐ Angina pectoris ☐ History of congestive heart failure ≤3 months, unless ejection fraction >40% ☐ Myocardial infarction ≤6 months prior to registration ☐ Cardiac arrhythmia ☐ Poorly controlled diabetes ☐ Interstitial pneumonia or extensive and symptomatic interstitial |

| fibrosis of the lung |
|--|
| Active or recent history of hemoptysis. If hemoptysis has resolved with |
| measures such as palliative radiation therapy (e.g. 3000 cGy over 10 |
| fractions), arteriographic embolization or endobronchial interventions (e.g. |
| photodynamic therapy, brachytherapy), etc. for >14 days, patients may be |
| considered for participation in this study. |
| ≥ Grade 2 hypertriglyceridemia |
| ≥ Grade 2 hypercholesterolemia |
| Any illness that in the opinion of the investigator would compromise the |
| ability of the patient to participate safely in the clinical trial. |
| |

- 3.27 Use of St. John's Wort because of its effects on hepatic drug metabolism.
- 3.28 Other active malignancy.

EXCEPTIONS: Non-melanoma skin cancer, localized prostate cancer, or carcinoma-in-situ of the cervix. NOTE: If there is a history or prior malignancy, patient must not be receiving other cytotoxic or molecularly targeted therapeutics treatment for their cancer. Patients receiving certain hormonal manipulations as part of their treatment may be allowed to continue at the discretion of the PI (e.g. LHRH analogs for prostate cancer).

3.29 Unable to discontinue use of potent CYP3A4 inhibitors/inducers (see appendix IV).

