4.0 Test Schedule

| | 1 | T | | 1 |
|--|------------------|------------------------|---------|------------------------|
| | ≤14 days | | | Prior to subsequent |
| | prior to | Weekly | | cycles |
| Tests and procedures | registration | $(\pm 2 \text{ days})$ | Cycle 1 | $(\pm 2 \text{ days})$ |
| History and exam, wt, PS | X | | X | X |
| Height | X | | | |
| Adverse event assessment | X | | | X |
| Tumor measurement (CT, PET/CT) | \mathbf{X}^{1} | | | X^2 |
| Hematology group WBC, ANC, Hgb, PLT | X | X^4 | X | X |
| Chemistry group Na, K, chloride, glucose, creatinine, total bilirubin, albumin, alkaline phosphatase, SGOT (AST), SGPT (ALT) | X | X ⁴ | X | X |
| Lipid Panel | XR | | | X8 |
| Urinalysis/urine protein dipstick | X | X^4 | X | X |
| Pregnancy Test | X ³ | | | |
| Patient Medication Diary for Sirolimus and Auranofin (Appendix II) ⁵ | | | X | X |
| Mandatory research tissue (see Section 17) ^{6,7} | X^R | | | |

- 1. Imaging studies such as chest x-ray, CT scans, and MRIs can be performed ≤30 days prior to registration. Use same imaging throughout the study. The CT portion of a PET CT can be considered interchangeable with a CT scan.
- 2. Tumor assessment must be performed at least every other cycle after completing Cycle

- 2;
- i.e. after Cycles 2, 4, 6, etc. Tumor assessment should be performed at any time during the treatment cycle that disease progression is clinically suspected so that patient can go off treatment and receive other therapy.
- 3. Women of childbearing potential only. Must be done \leq 7 days prior to registration.
- 4. Weekly during cycle 1 only.
- 5. The diary must begin the day the patient starts taking the medication and must be completed per protocol and returned to the treating institution OR compliance must be documented in the medical record by any member of the care team.
- 6. Tissue specimens must be collected and submitted *once at baseline*.
- 7. Optional repeat biopsy of accessible tumor at response and/or disease progression.
- 8. Lipid panel is performed at baseline, prior to cycle 2, every other cycle through cycle 6, and then as clinically indicated (per Standard of Care) thereafter.
- 9. R Research funded (see Section 19.0).

5.0 Grouping Factor:

5.1 Phase: Phase I vs Phase II.

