6.3 Phase I and II

6.31 Correlative Research

Mandatory

A mandatory correlative research component is part of this study, the patient will be automatically registered onto this component (see Sections 3.19c and 17.0).

Optional

An optional correlative research component is part of this study: there will be an option to select if the patient is to be registered onto this component (see Section 17.0).

- Patient has/has not given permission to give his/her *tissue* sample for research testing as a part of this study (see section 17.0).
- 6.32 Prior to accepting the registration, registration/randomization application will verify the following:
 - IRB approval at the registering institution
 - Patient eligibility
 - Existence of a signed consent form
 - Existence of a signed authorization for use and disclosure of protected health information
- 6.33 Documentation of IRB approval must be on file in the Registration Office before an investigator may register any patients.

In addition to submitting initial IRB approval documents, ongoing IRB approval documentation must be on file (no less than annually) at the Registration Office ([contact]). If the necessary documentation is

not submitted in advance of attempting patient registration, the registration will not be accepted and the patient may not be enrolled in the protocol until the situation is resolved.

When the study has been permanently closed to patient enrollment, submission of annual IRB approvals to the Registration Office is no longer necessary.

- 6.34 At the time of registration, the following will be recorded:
 - Patient has/has not given permission to store and use his/her sample(s) for future research of Non-small cell lung cancer at Mayo.
 - Patient has/has not given permission to store and use his/her sample(s) for future research to learn, prevent, or treat other health problems.
 - Patient has/has not given permission for MCCC to give his/her sample(s) to researchers at other institutions.
- 6.35 Treatment on this protocol must commence at Mayo Clinic Arizona institution under the supervision of a medical oncologist.
- 6.36 Treatment cannot begin prior to registration and must begin \Box 14 days after registration.
- 6.37 Pretreatment tests/procedures (see Section 4.0) must be completed within the guidelines specified on the test schedule.
- 6.38 All required baseline symptoms (see Section 10.3) must be documented and graded.

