7.0 Protocol Treatment

7.1 Treatment Schedule

7.11 Phase I Cohort:

| Agent | Dose Level | Route | Day | ReRx |
|-----------|---------------------|-------|-----------------------------------|------|
| Auranofin | As assigned by | PO | PO Daily | |
| | Registration office | | | days |
| Sirolimus | 5 mg | PO | Daily (cycle 1 only, begin day 8, | Q28 |
| | | | subsequent cycles begin day 1) | days |

7.12 Phase 2 Cohort (at MTD from Phase I):

| Agent | Dose Level | Route | Day | ReRx |
|-----------|--------------------|-------|-----------------------------------|------|
| Auranofin | As determined by | PO | Daily | Q28 |
| | studies in Phase I | | | |
| Sirolimus | olimus 5 mg PO | | Daily (cycle 1 only, begin day 8, | Q28 |
| | | | subsequent cycles begin day 1) | days |

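### The only pregnancy test is timed to registration, so the plan permits a first auranofin dose on a test up to 21 days old; a conditional pre-dose repeat would be a cheap safety improvement

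*Combined protocol and SAP*

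**What the plan says.** All references are to the combined protocol and SAP.

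- **3.17** asks for a negative serum pregnancy test at most "7 days prior to registration, for women of childbearing potential only".
- **4.0, footnote 3** sets the same limit: "Women of childbearing potential only. Must be done" no more than 7 days before registration. The pregnancy test row has one mark, in the screening column. Its weekly, Cycle 1 and later-cycle cells are empty.
- **6.32** has eligibility checked before a registration is accepted: "Prior to accepting the registration, registration/randomization application will verify the following", with eligibility on the list that follows.
- **6.36** reads "Treatment cannot begin prior to registration and must begin", followed by a lost sign and 14 days after registration.
- **6.37** says that pretreatment tests "must be completed within the guidelines specified on the test schedule". It points back to 4.0 and adds no test of its own.
- **7.1** lists auranofin as daily with no delayed start. Sirolimus is "Daily (cycle 1 only, begin day 8".
- **3.21** gives the reason for excluding pregnant women: "this study involves an agent that has known genotoxic, mutagenic and teratogenic effects". It also excludes "Men or women of childbearing potential who are unwilling to employ adequate contraception".

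**The concern.** The test is anchored to registration, while the risk begins at the first dose. A treatment-start window lies between the two, and no scheduled test falls inside it. A pregnancy too early to show at screening, or one begun before treatment starts, would not be picked up by any scheduled test before dosing.

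The plan's own choices suggest that its authors wanted a recent result. Section 3.15 lets the screening blood counts and chemistry be 14 days old at registration, but 3.17 allows the pregnancy test only 7. In 4.0, hematology, chemistry and urinalysis are repeated at Cycle 1, and the pregnancy test is not.

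What is at stake is fetal exposure in a rare case. The exposure could not be ended quickly by stopping the drug: 15.15 gives gold a half-life of 21 to 31 days in blood and 42 to 128 days in tissue. The moment before the first dose is therefore when a test result is most useful.

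**Working it through.** The plan states no figure for the age of the test at dosing, so there is none to reproduce. The check adds the permitted windows.

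**Inputs**

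| Input | Value | Source |
|---|---|---|
| Test to registration | at most 7 days | 3.17; 4.0 footnote 3 |
| Registration to first treatment | at most 14 days (sign assumed) | 6.36 |
| First auranofin dose | day 1 | 7.1 |
| First sirolimus dose | day 8, which is 8 − 1 = 7 days later | 7.1 |
| Women expected | 19 of 47 | 16.73 |
| Accrued / evaluable, efficacy portion | 41 / 37 | 16.12 |

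**Maximum test age under the plan**

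- First auranofin: 7 + 14 = 21 days.
- First sirolimus: 21 + 7 = 28 days.

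**The lost sign.** The placeholder itself does not settle the reading: elsewhere in section 3 the same mark stands where an upper limit is meant (transaminases, 3.15) and where a lower limit is meant (life expectancy, 3.19a). The sense of 6.36 settles it. The sentence first bars treatment before registration and then says by when treatment must begin. If the limit were strictly less than 14 days, the maximum in whole days would be 7 + 13 = 20. If it were a minimum, every test would be at least 14 days old at the first dose, with no ceiling. The gap exists on every reading.

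**Maximum test age with a repeat required once the screening test is over 7 days old**

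- First auranofin: 7 days.
- First sirolimus: 7 + 7 = 14 days.

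**Number of repeat tests.** The lower bound is 0. The upper bound is 19 (19/47 = 40%), reached only if every woman expected is of childbearing potential and starts more than 7 days after her test. The documents give neither proportion.

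**Effect on the statistics.** Section 16.31 counts eligible, consented patients who have begun treatment. A woman with a positive repeat before dosing is untreated, so she does not enter the primary endpoint. Section 16.12 already leaves 41 − 37 = 4 places for cancellations, ineligible patients and major violations. The endpoint definition, the 37-patient decision rule, its power and its significance level are unchanged.

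**The case against.** The strongest reply is that this is a preference. Sections 3.17 and 4.0 agree with each other, and nothing in the plan sets a maximum test age at dosing. The 21 days needs the earliest permitted test and the latest permitted start in the same patient. The plan also has other protection: the contraception requirement in 3.21, the Cycle 1 history and exam in 4.0, and the weekly cycle 1 visits in 7.4. The teratogenicity premise rests on one sentence that names no agent, and the adverse event lists in 15.17 and 15.27 show no reproductive effect.

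Much of this stands. Two stronger readings are tempting, and the documents support neither. A reader might infer that 3.17 and 6.36 contradict each other. They do not: one governs eligibility at registration, the other the start of treatment. A reader might also infer that women will usually be dosed on tests about three weeks old. The plan gives no typical interval from registration to first dose, so nothing can be said about frequency.

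The other safeguards lower the risk without closing the gap. Willingness to use contraception is not evidence that a woman is not pregnant. The Cycle 1 exam includes no pregnancy test and is not stated to precede dosing. The weekly visits take place during treatment. Sections 15.17 and 15.27 also defer to package inserts for complete information, so their silence does not undo the reason that 3.21 gives.

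Two objections bear on the remedy. First, a 7-day limit still leaves some chance of a missed early pregnancy, and it adds no test on treatment. That is true: the repeat narrows the gap and does not remove it. Second, a positive repeat cannot always be handled as a cancel under 13.8, which ends data submission. A woman already pregnant at registration met an exclusion, so 13.6 makes her ineligible and requires event monitoring even if she was never treated. The rule has to separate the two cases.

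**Conclusion.** The point holds as a minor safety improvement. The plan, followed exactly, permits a first auranofin dose on a pregnancy test up to 21 days old and a first sirolimus dose on one up to 28 days old. This rests on reading the lost sign in 6.36 as an upper limit and on auranofin starting on day 1. The number of women it could affect lies between 0 and 19, is not stated, and is probably small. Zero cannot be excluded. It is not a breach, an internal conflict or a statistical defect.

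**What to change.** Leave 3.17 as it is, because 6.32 and 13.6 judge eligibility at registration. Add this rule to 6.36/6.37 and to footnote 3 of 4.0:

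> For women of childbearing potential, if the screening test will be more than 7 days old at the first dose of study treatment, a repeat serum pregnancy test within 7 days before that dose must be negative, with the result known before dosing. If it is positive, no study treatment is given; the patient is classified as ineligible under 13.6 if she is judged to have been pregnant at registration, and otherwise as a cancel under 13.8.

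Mark the Cycle 1 cell of the pregnancy test row: pre-dose, if applicable. The 7-day limit is taken from 3.17.

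The cost is one rule in two places, one table mark, and one extra serum test in each woman who starts more than 7 days after screening. Section 4.0 does not say that the Cycle 1 bloods are drawn before dosing, so a separate draw or a short wait for the result may be needed. Nothing in section 16.0 has to change.

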4.0 Test Schedule

| | 1 | T | | 1 |
|--|------------------|------------------------|---------|------------------------|
| | ≤14 days | | | Prior to subsequent |
| | prior to | Weekly | | cycles |
| Tests and procedures | registration | $(\pm 2 \text{ days})$ | Cycle 1 | $(\pm 2 \text{ days})$ |
| History and exam, wt, PS | X | | X | X |
| Height | X | | | |
| Adverse event assessment | X | | | X |
| Tumor measurement (CT, PET/CT) | \mathbf{X}^{1} | | | X^2 |
| Hematology group WBC, ANC, Hgb, PLT | X | X^4 | X | X |
| Chemistry group Na, K, chloride, glucose, creatinine, total bilirubin, albumin, alkaline phosphatase, SGOT (AST), SGPT (ALT) | X | X ⁴ | X | X |
| Lipid Panel | XR | | | X8 |
| Urinalysis/urine protein dipstick | X | X^4 | X | X |
| Pregnancy Test | X ³ | | | |
| Patient Medication Diary for Sirolimus and Auranofin (Appendix II) ⁵ | | | X | X |
| Mandatory research tissue (see Section 17) ^{6,7} | X^R | | | |

- 1. Imaging studies such as chest x-ray, CT scans, and MRIs can be performed ≤30 days prior to registration. Use same imaging throughout the study. The CT portion of a PET CT can be considered interchangeable with a CT scan.
- 2. Tumor assessment must be performed at least every other cycle after completing Cycle

- 2;
- i.e. after Cycles 2, 4, 6, etc. Tumor assessment should be performed at any time during the treatment cycle that disease progression is clinically suspected so that patient can go off treatment and receive other therapy.
- 3. Women of childbearing potential only. Must be done \leq 7 days prior to registration.
- 4. Weekly during cycle 1 only.
- 5. The diary must begin the day the patient starts taking the medication and must be completed per protocol and returned to the treating institution OR compliance must be documented in the medical record by any member of the care team.
- 6. Tissue specimens must be collected and submitted *once at baseline*.
- 7. Optional repeat biopsy of accessible tumor at response and/or disease progression.
- 8. Lipid panel is performed at baseline, prior to cycle 2, every other cycle through cycle 6, and then as clinically indicated (per Standard of Care) thereafter.
- 9. R Research funded (see Section 19.0).

5.0 Grouping Factor:

5.1 Phase: Phase I vs Phase II.

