7.22 MTD Determination

MTD is defined as the dose level below the lowest dose that induces doselimiting toxicity in at least one-third of patients (at least 2 of a maximum of 6 new patients).

7.221 Three patients will be treated at a given dose level combination and observed for at least 1 cycle to assess toxicity (accrual will be suspended while the 3 patients are treated and observed).

- 7.222 If dose-limiting toxicity (DLT) is not seen in any of the 3 patients, 3 new patients will be accrued and treated at the next higher dose level. If DLT is seen in 2 or 3 of 3 patients treated at a given dose level, then the next 3 patients will be treated at the next lower dose level, if only 3 patients were enrolled and treated at this lower dose level.
- 7.223 If DLT is seen in 1 of 3 patients treated at a given dose level, up to 3 additional patients will be enrolled and treated at the same dose level (accrual will be suspended while the 3 patients are treated and observed). If DLT is seen in at least one of these additional three patients (≥2 of 6), the MTD will have been exceeded and further accrual will cease to this cohort. If DLT is not seen in any of the three additional patients, 3 new patients will be accrued and treated at the next higher dose level.
- 7.224 After enrolling 6 patients on a specific dose level, if DLT is observed in at least 2 of 6 patients, then the MTD will have been exceeded and defined as the previous dose unless only 3 patients were treated at the lower dose level. In that case, 3 additional patients will be treated at this lower dose level.
- 7.23 Dose Escalation: Doses will not be escalated in any individual patient.
- 7.24 If a patient fails to complete Cycle 1 for reasons other than toxicity, the patient will be regarded as treatment intolerant and an additional patient will be treated at the current dose level.
- 7.3 Patients can be instructed in administration techniques for both sirolimus and auranofin and granted treatment independence.
- 7.4 Patient must return to Mayo Clinic for evaluation at least every week during the first cycle of treatment and then at least every 4 weeks.
- 7.5 Study treatment by a local medical doctor (LMD) is not allowed.

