8.0 Dosage Modification Based on Adverse Events

Strictly follow the modifications in this table for the first **two** cycles, until individual treatment tolerance can be ascertained. Thereafter, these modifications should be regarded as guidelines to produce mild-to-moderate, but not debilitating, side effects. If multiple adverse events are seen, administer dose based on greatest reduction required for any single adverse event observed. Reductions or increases apply to treatment given in the preceding cycle and are based on adverse events observed since the prior dose.

ALERT: ADR reporting may be required for some adverse events See Section 10

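### The lipid panel schedule skips the evaluation before cycle 3, which closes the strict dose-rule period, and disagrees with Sections 10.3 and 19.2

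*Combined protocol and SAP*

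**What the plan says.** Four parts of the protocol bear on lipid monitoring.

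- **Test schedule (4.0).** Footnote 8 reads: "Lipid panel is performed at baseline, prior to cycle 2, every other cycle through cycle 6, and then as clinically indicated". The adverse event row, "Adverse event assessment | X | | | X", marks baseline and the visit before every later cycle, with no alternate-cycle footnote. The blood chemistry drawn before each cycle is "Chemistry group Na, K, chloride, glucose, creatinine, total bilirubin, albumin, alkaline phosphatase, SGOT (AST), SGPT (ALT"); it contains no cholesterol or triglycerides. Footnote 2 places tumor assessments "i.e. after Cycles 2, 4, 6, etc".
- **Grading list (10.3).** High cholesterol and hypertriglyceridemia are both marked for grading at baseline and at each evaluation.
- **Dose rules (8.0 and 8.2).** For either lipid event, Grade 2 means holding treatment until Grade 1, and stopping both drugs if that takes more than four weeks. Grade 3 or 4 means stopping both drugs. The table is strict for the first two cycles, "until individual treatment tolerance can be ascertained. Thereafter, these modifications should be regarded as" guidelines.
- **Budget (19.2).** The research-funded lipid panels are those at baseline and cycles 2, 3 and 4.

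**The concern.** The test schedule, the grading list and the budget do not describe the same monitoring. Both lipid grades are laboratory grades, and the lipid panel is their only scheduled source. Before cycles 3 and 5 a site is asked for the grades without a scheduled result. The protocol does not say what to record then: the last known grade, Grade 0 or a blank.

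This is more than form-filling because a grade can stop treatment. Section 15.27 counts both lipid events among the common or severe toxicities of sirolimus, and 15.294 sends nurses back to the protocol for the monitoring times. A patient below Grade 2 before cycle 2 who reaches Grade 3 or 4 in cycle 2 could continue both drugs until the panel before cycle 4. A patient who leaves at the first scan has no later scheduled panel: 18.0 asks for an adverse event form at end of treatment, but 4.0 sets no lipid test for that point. Such an event would be missing from the maximum-grade tables (16.52). If it were Grade 4 and at least possibly related, it would also be missing from the count for the stopping rule (16.532).

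**Working it through.** The plan states no figure to reproduce. The check sets the schedules side by side.

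**Inputs.** Cycle length is 28 days (Schema). Panel times come from 4.0 footnote 8 and from 19.2. Evaluations fall before every cycle (4.0, adverse event row; 7.4). The window is ±2 days (4.0). The maximum accrual is 47 (16.12).

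**Evaluation days.** The evaluation before cycle k falls at day 28 × (k − 1).

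| Evaluation before | Day | Footnote 8 | 19.2 list | Proposed |
|---|---|---|---|---|
| Cycle 2 | 28 | yes | yes | yes |
| Cycle 3 | 56 | **no** | yes | yes |
| Cycle 4 | 84 | yes | yes | yes |
| Cycle 5 | 112 | **no** | **no** | yes |
| Cycle 6 | 140 | yes | **no** | yes |
| Covered | | 3 of 5 | 3 of 5 | 5 of 5 |

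**Gap under footnote 8.** 84 − 28 = 56 days, and 140 − 84 = 56 days. With ±2 days at each end the range is 52 to 60. At full dosing, 28 + 28 = 56 daily sirolimus doses fall between the first two on-treatment panels. The time limit in the Grade 2 rule is four weeks, so the gap is twice that limit.

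**Gap under the proposal.** 56 − 28 = 28 days, range 24 to 32.

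**If a site followed both footnote 8 and 19.2.** Panels would fall at days 28, 56, 84 and 140. Only the evaluation before cycle 5 would be uncovered, and the longest gap would still be 140 − 84 = 56 days.

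**Why cycle 3 matters more.** The evaluation at day 56 looks back over cycle 2, the second of the two strict cycles in 8.0. It also falls at the first scan, after cycle 2. Under footnote 8, a patient who stops there has one scheduled on-treatment value, taken before cycle 2 began. The evaluation before cycle 5 coincides with the second scan, but by then 8.2 is only guidance.

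**Extra panels.** 2 per patient × 47 patients = 94 at most, if all reach cycle 5.

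**The case against.** The best defense is that footnote 8 is a deliberate plan: one early panel, then alternate cycles, then clinical judgment. Section 10.3 is a list for grading and reporting; tests are set in 4.0. A reader might infer that 10.3 obliges a panel at every visit, so that footnote 8 breaches the protocol. The documents do not support that. Section 10.3 orders no tests and can be followed using the results in hand. It also has no cut-off, so the same reading would demand panels at every visit after cycle 6, which is not proposed here. This part of the objection stands: 10.3 alone does not settle the matter.

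There are real safeguards too.

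- Section 3.26 excludes "≥ Grade 2 hypertriglyceridemia" and the same grade of cholesterol at entry. That limits starting risk, not later rises.
- Sirolimus is given "Daily (cycle 1 only, begin day 8", so the panel before cycle 2 follows 21 daily doses (days 8 to 28). With the 62-hour half-life in 15.25, five half-lives take 5 × 62 / 24 = 12.9 days, so exposure is near steady state by then in most patients. With the 113 hours given for hepatic impairment it is 23.5 days. Steady drug levels make a late lipid rise less typical but do not exclude it.
- Patients return "at least every week during the first cycle of treatment and then at least every 4 weeks" (7.4), and an unscheduled panel is always possible. A patient already on hold for Grade 2 needs repeat tests anyway.

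These points reduce the consequence. They do not explain why 19.2 pays for a cycle 3 panel that footnote 8 does not schedule, and they do not supply a lipid value at the end of cycle 2.

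**Conclusion.** The point holds as a minor inconsistency with a cheap remedy. Under footnote 8, 2 of 5 evaluations before cycles 2 to 6 have no scheduled lipid result, and scheduled panels are 56 days apart. The gap before cycle 3 carries most of the weight; the gap before cycle 5 carries little.

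This rests on three assumptions: that footnote 8 means cycles 2, 4 and 6 (any alternate-cycle reading leaves some evaluation uncovered); that sites follow 4.0 and not 19.2; and that cycles run without delay.

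A reader might go further and infer that a measurable share of sirolimus exposure is unmonitored, or that the stopping rule is materially weakened. The documents do not support either. A panel is a reading at one time and does not cover a fraction of doses. The plan gives no lipid event rate, so neither the number of missed events nor the effect on the rule can be calculated. Nor does the gap reach phase I dose decisions, since lipid events are not on the dose-limiting toxicity list in 7.213. The primary endpoint, 4-month progression-free survival, does not require a patient to be on treatment (16.31), and the sample size and error rates are unchanged.

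**What to change.** Amend footnote 8 so that the lipid panel is done at baseline, before each of cycles 2 to 6, and after that on clinical grounds as now. Run it on the chemistry sample already drawn before each cycle. Make 19.2 list the same times. If only one panel can be added, it should be the one before cycle 3, which 19.2 already lists. Section 8.2 and the arrangement after cycle 6 can stay as they are.

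The cost is a protocol amendment and at most two extra panels per patient: no more than 94 over 47 patients, and fewer as patients leave treatment. Of these, the cycle 3 panels are already on the funded list. Funding for cycle 5 must be found, and funding for cycle 6, which footnote 8 already schedules but 19.2 omits, must be settled. The estimate assumes that the lipid test can share the existing draw.
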